4. STUDY DESIGN

This is a single-center, randomized, sham-controlled, double-blind clinical study to investigate the feasibility of delivering RS-tDCS sessions for high-risk patients for suicide in the days following discharge from the CPEP or inpatient unit which they were admitted with SI or attempt. We plan to assess up to 80 adult patients for eligibility over 12 months of which 20 will be enrolled and randomized. Clinical assessments will be performed at baseline, post-treatment day 14 (14 days after the first RS-tDCS session), and follow-up day 30 and 60 (30 and 60 days after the first RS-tDCS session, respectively).

All study outcome measures are described in Table 1.

Time points		in-person	remote	
	Measures		S1 to S10	C14, C30, and C60
Eligibility screening		Х		
Informed consent		Х		
Enrollment		Х		
		Baseline		
Demographic data		Х		
General medical history		X		
Orientation tDCS session		X		
Loan agreement		Х		
	Feasibility		X*	
	C-SSRS	X		Х
	RRS	X		Х
	CAST	Х		Х
	MADRS	Х		Х
	C-SSRS SV		X	
	Side effects questionnaire		X	
	Treatment emergent event review		Х	Х
	Acceptability questionnaire		X**	
	Blinding assessment		X**	

Table 1. Study's time points and measures.

C14, C30, and C60: clinical assessments at post-treatment day 14, follow-up day 30 and follow-up day 60; CAST: The Concise Associated Symptoms Tracking; C-SSRS: The Columbia-Suicide Severity Rating Scale; C-SSRS SV: The Columbia-Suicide Severity Rating Scale – screening version; MADRS: Montgomery-Asberg Depression Rating Scale; RRS: Ruminative Responses Scale; S1 to S10: remotely supervised transcranial direct current stimulation (RS-tDCS) sessions one to ten.

*Number of completed RS-tDCS sessions per participant within three weeks of the study.

**applied only once, after the final RS-tDCS session (the tenth session).

Primary outcome measures:

Page 5 of 22 Version Date: 10/09/2023 1. Feasibility of the intervention – number of completed remotely supervised transcranial direct current stimulation (RS-tDCS) sessions, for both active and sham groups:

We expect at least 70% of the subjects to complete at least 5 of recommended 10 RS-tDCS sessions within three weeks of receiving the home-based tDCS device.

This criterion is based on a study that reported dropout rates between 22% and 25% of homebased tDCS for patients with bipolar depression (40) and that therapeutic effects with tDCS could be achieved within one week of treatment (24).

Secondary outcome measures:

1. Intensity of suicidal ideation as assessed by the Columbia Suicide Severity Rating Scale (C-SSRS) (41) (time frame: day 14 [+ 7 days], day 30 [+ 7 days], and day 60 [+ 10 days] from the first RS-tDCS session):

The C-SSRS is a suicidal ideation and behavior rating scale with yes/no responses. For each of the 5 items of the C-SSRS related to suicidal ideation intensity, an individual's degree of suicidal ideation is rated on a 0-5 scale. The total score is the sum of the 5 intensity item scores (total score ranges from 0 to 25), with higher scores indicating more severe suicidal ideation.

2. Acceptability based on subject's readiness, self-confidence, and satisfaction in dealing with the device and RS-tDCS sessions. Acceptability based on subject's readiness, self-confidence, and satisfaction will be considered if at least 60% of all subject's rate "strongly agree" or "agree" on the questionnaire item 11: "Overall, I felt that transcranial electrical stimulation treatment benefited me" (the questionnaire is a 5-item Likert scale with the following response options "Strongly agree", "Agree", "Neither agree nor disagree", "Disagree", "Strongly disagree") (42). These questions were adapted from other studies with home-based tDCS (37, 43) and will be presenting as following: 1) "It was easy to prepare the device and accessories"; 2) "I felt confident setting up the stimulation sessions"; 3) "I felt confident using the device"; 4) "I needed to learn a lot of things before I could get going with this device"; 5) "The device was unnecessarily complex"; 6) "I could find a convenient time to do the stimulation sessions"; 7) "I would imagine that most people would learn to use this device quickly"; 8) "The stimulation sessions interfered with my everyday life"; 9) "It would have helped to have more in-person, one-on-one instruction"; 10) "I felt that the remote supervision sessions were helpful"; 11) "Overall, I felt that transcranial electrical stimulation treatment benefited me". Questions 4, 5, 8, and 9 will be reverse coded. This information will be collected after the final RS-tDCS session (that is, the tenth RS-tDCS session).15

3. Proportion of patients who answered "no" for both questions 1 ("Have you wished you were dead or wished you could go to sleep and not wake up?") and 2 ("Have you actually had any thoughts of killing yourself?") of the C-SSRS (time frame: day 14 [+ 7 days], day 30 [+ 7 days], and day 60 [+ 10 days] from the first RS-tDCS session). This will help to determine the proportion of subjects who presented suicidal ideation relapse since the negative answer for both questions will be an inclusion criterion for this study.

4. Intensity of rumination as assessed by the Ruminative Responses Scale (RRS) (44) (time frame: day 14 [+ 7 days], day 30 [+ 7 days], and day 60 [+ 10 days] from the first RS-tDCS session):

The RRS encompasses 22 items. Each item is rated on a 4-point Likert scale: 1, almost never; 2, sometimes; 3, often; 4, almost always. The score on this scale is obtained by simply summing the scores on the 22 items.

5. Symptoms associated with suicidal ideation as assessed by the Concise Associated Symptoms

Tracking (CAST) scale (time frame: day 14 [+ 7 days], day 30 [+ 7 days], and day 60 [+ 10 days] from the first RS-tDCS session):

The 16 items of the CAST Scale assess symptoms across five domains: anxiety (three items, subscore range 3-15), irritability (five items, subscore range 5-25), mania (four items, subscore range 4-20), insomnia (two items, subscore range 2-10), and panic (two items, subscore range 2-10). The total CAST score ranges from 16 to 80. Each item is rated on a 5-point Likert scale: 1, strongly disagree; 2, disagree; 3, neither agree nor disagree; 4, agree; or 5, strongly agree, with higher scores indicating more severe symptoms.

6. Depressive symptoms as assessed by the Montgomery-Asberg Depression Rating Scale (MADRS) (time frame: day 14 [+ 7 days], day 30 [+ 7 days], and day 60 [+ 10 days] from the first RS-tDCS session):

MADRS is a 10-item questionnaire that includes questions on the following symptoms: 1. Apparent sadness 2. Reported sadness 3. Inner tension 4. Reduced sleep 5. Reduced appetite 6. Concentration difficulties 7. Lassitude 8. Inability to feel 9. Pessimistic thoughts 10. Suicidal thoughts. Each item yields a score of 0 to 6. The overall score ranges from 0 to 60. A higher MADRS score indicates more severe depression. The usual cutoff points are:

0 to 6 - normal/symptom absent; 7 to 19 - mild depression; 20 to 34 - moderate depression; >34 - severe depression.

7. The level of side effects will be assessed at the end of each session on a 0 (not at all) to 10 (highest degree) scale used by Ahn et al. (2019) (37), which includes the following symptoms: 1. Itching; 2. Burning; 3. Headache; 4. Fatigue; 5. Nervousness; 6. Dizziness; 7. Difficulty concentrating. The total score is the sum of the 7 items, varying from 0 to 70. Higher scores indicate higher levels of side effects.

8. Treatment emergent event review: after each RS-tDCS session and clinical assessment, subjects will be asked "Have you had any new symptoms, new medical conditions or been started on new medication/treatment since we last saw you?". This information will help research staff to judge about potential adverse events related to the trial. In addition, changes in treatment will help researchers to account for them in data analysis and the study's results interpretation.

4.1. **STUDY INTERVENTION**

The study intervention is tDCS treatments delivered by the Soterix Medical mini-CT device (https://soterixmedical.com/research/remote/mini-CT). The device is a nonsignificant risk (NSR) device study because it does not meet the definition of a significant risk device under §812.3 (m) of the investigational device exemptions (IDE) regulation (21 CFR §812)

(https://www.accessdata.fda.gov/scripts/cdrh/cfdocs/cfcfr/CFRSearch.cfm?fr=812.3).

The Soterix Medical mini-CT device for the RS-tDCS includes: (1) 1 x 1 mini-CT tDCS device; (2) SNAPstrap headgear, a "cap"-like placement for simple positioning and uniform electrode placement; (3) SNAPpads (individually-packaged pre-moistened sponge), and snap connectors (Figure 1) (39).

[figure not shown]

Figure 1. Remotely supervised (RS-tDCS) Equipment. (1) 1 x 1 mini-CT tDCS device; (2) SNAPstrap headgear: "cap"-like placement for simple positioning and uniform electrode placement; (2a) markers for guidance in placement; (2b) electrode polarity labeling with fixed wiring. (3) SNAPpad: (3a) individually-packaged pre-moistened sponge; perforated packaging for easy opening; (3b) snap connectors. (adapted from Pilloni, G., A. et al., Brain Stimul 15(3): 707-716, http://creativecommons.org/licenses/by-nc-nd/4.0/, DOI: 10.1016/j.brs.2022.04.014). The figure at the bottom simulates an RS-tDCS session.

Subjects will be randomized 1:1 to either active or sham RS-tDCS. The active RS-tDCS delivers a constant current intensity of 2mA on the subject's scalp, with SNAPstrap headgear and 5x7 (35cm2) SNAPpads positioning bilaterally (anodal-left and cathodal-right), on the DLPFC, for 30 minutes. A similar protocol's administration was found effective, safe, and tolerable as an add-on intervention to decrease depressive symptoms in patients with bipolar depression (45). Sham tDCS looks identical to a typical RS-tDCS cap but delivers a 30-second ramp-up (0-2 mA) stimulation followed by a 30-second rampdown (2-0 mA) at the beginning and end of the application. Figure 2 shows a representation of the electric current delivered by the active and sham RS-tDCS.

[figure not shown]

Figure 2. Stimulation protocol. Active tDCS (upper) and sham tDCS (lower).

The tolerability and safety of home-based tDCS were assessed over 6,779 sessions from six clinical trials. Sessions were administered daily, with treatment ranging from 10 to 60 sessions per subject. The authors reported no serious adverse events, a similar proportion of tingling (68%), itching (41%), and warmth sensation (42%) between active and sham groups, and no participant discontinuation due to lack of tolerability (39).

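### Acceptability and blinding are asked only after session 10, so early stoppers are not asked, and the 60% acceptability verdict rests on perceived benefit pooled with sham

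*Combined protocol and SAP*

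**What the plan says.** Secondary outcome 2 in Section 4 (Study Design) is named "Acceptability based on subject's readiness, self-confidence, and satisfaction in dealing with the device and RS-tDCS sessions". Acceptability "will be considered if at least 60% of all subject's rate" one of the two agreeing categories on item 11, which reads "Overall, I felt that transcranial electrical stimulation treatment benefited me". Items 1 to 10 cover preparation, confidence, complexity, convenience, instruction and supervision. Four of them are reverse coded, but none enters the rule.

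On timing, secondary outcome 2 states: "This information will be collected after the final RS-tDCS session (that is, the tenth RS-tDCS session"). The Table 1 footnote for both the acceptability questionnaire and the blinding assessment says "applied only once, after the final RS-tDCS session (the tenth session"). Section 8 (Study Procedures) gives the same timing, calls the instrument the feasibility questionnaire, and ties return of the device to the same session. Table 1 schedules neither instrument at day 14, 30 or 60.

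The primary outcome expects "at least 70% of the subjects to complete at least 5 of recommended 10 RS-tDCS sessions" within three weeks of receiving the device. Section 17 (Data Analysis Plan) gives no rule for missing acceptability or blinding answers.

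**The concern.** There are two separate problems.

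**Who is asked.** All three places define the final session as the tenth, so it cannot be read as each subject's own last session. No contact at the end of sessions is described for someone who stops earlier. A subject can thus be a success on the primary outcome and never be asked about acceptability or treatment guess. Section 2 motivates the trial by poor engagement and dropout after discharge, so those who stop are among the most informative about acceptability.

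**What the verdict measures.** The outcome is named for readiness, self-confidence and satisfaction in handling the device and sessions, but the decision rests on whether the subject felt helped. Pooling the arms suits usability, since Aim 1 also covers the sham protocol. For perceived benefit, pooling makes the verdict depend on sham response. Subjects could find the device easy and the rule still fail, or the reverse.

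**Working it through.** **Inputs from the plan.** 20 randomised 1:1 (Sections 4 and 4.1), taken as 10 per arm; a 60% cut-off on item 11; feasibility success at 5 of 10 sessions; and "a study that reported dropout rates between 22% and 25"% (Section 4, repeated in Section 17). The plan gives no derivation of the 60% cut-off or of the sample size, so there is no derived figure to reproduce.

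**Assumptions.** The cited dropout is equated with not reaching session 10: 20 × (1 − 0.22) = 15.6 and 20 × (1 − 0.25) = 15, so 15 or 16 are asked. Agreement rates are illustrative.

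**Step 1: literal denominator.** 0.60 × 20 = 12 must agree. With m asked, the share needed is 12/m and the chance of passing at 70% agreement is P(Bin(m, 0.7) ≥ 12).

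| Asked (m) | Share needed | Chance of passing |
|---|---|---|
| 20 | 60% | 0.887 |
| 18 | 67% | 0.722 |
| 16 | 75% | 0.450 |
| 15 | 80% | 0.297 |

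**Step 2: what asking everyone would give.** The 0.887 assumes that stoppers agree as often as completers. Let m completers agree at 70% and 20 − m stoppers at rate s, and compute P(Bin(m, 0.7) + Bin(20 − m, s) ≥ 12).

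| Completers | s = 20% | s = 40% | s = 70% |
|---|---|---|---|
| 15 | 0.507 | 0.689 | 0.887 |
| 16 | 0.606 | 0.738 | 0.887 |

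**Step 3: respondents-only denominator.** The number needed is 0.6m rounded up: 9 of 15, 10 of 16, 11 of 18. At 70% agreement the chances are 0.869, 0.825 and 0.859.

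**Step 4: dependence on sham.** With all 20 answering and all 10 active subjects agreeing, 12 − 10 = 2 sham subjects must still report benefit. P(Bin(10, a) + Bin(10, b) ≥ 12), with a and b the assumed agreement rates in the active and sham arms:

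| Active | Sham 20% | Sham 40% | Sham 60% |
|---|---|---|---|
| 60% | 0.040 | 0.247 | 0.596 |
| 80% | 0.197 | 0.602 | 0.892 |
| 90% | 0.368 | 0.798 | 0.969 |

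**Step 5: blinding.** Suppose an arm of 10 has 4 correct guesses, 4 wrong and 2 unasked. The observed Bang index is 0. The two missing guesses could move it to (4 − 6)/10 = −0.2 or (6 − 4)/10 = +0.2. The exact 95% interval for 4 of 8 correct is 0.157 to 0.843, which as 2p − 1 is about −0.69 to +0.69. Sampling error dominates.

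**The case against.** **Denominator.** A reader might infer that unasked subjects can only count against the rule. That holds under the literal wording. All subjects could also be meant as both arms together, and no missing-answer rule settles it. With respondents only, the chance of passing barely moves (82% to 87% against 89%). The selection problem remains, though: the verdict would then rest on ten-session completers and probably lean favourable.

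**Size of the loss.** A reader might take the fall from 89% to 30% or 45% as what asking everyone would recover. Step 2 shows it can be much less, and subjects who withdrew would stay unasked.

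**Subjects with 5 to 9 sessions.** It would be too strong to say that anyone with 5 to 9 sessions at three weeks is never asked. The three-week limit belongs to the feasibility count, "Number of completed RS-tDCS sessions per participant within three weeks of the study", and nothing in the plan ends sessions there. Such a subject may still reach session 10.

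**Item 11 and arms.** Item 11 is the one overall item and may bear on satisfaction. Reverse coding suggests that items 1 to 10 will be scored, so usability data are not lost. Section 17 compares groups at each established time point, which arguably already covers item 11 by arm. These points stand. They leave a mismatch between the label and the verdict, not an absence of data, and they favour relabelling over replacing a prespecified rule with a new cut-off.

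**Conclusion.** The concern holds in this form. Followed as written, the plan gives an acceptability verdict from a selected group, under a label that the deciding item does not match. On the literal denominator with 15 or 16 asked, the chance of passing at 70% agreement is 30% or 45%. With all 20 asked it is 89% if stoppers agree equally often and about 51% to 74% if they agree at 20% to 40%. These figures rest on the assumed agreement rates and on equating the cited dropout with not reaching session 10.

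A reader might infer that the feasibility result or a go/no-go decision is compromised. The documents do not support that: the primary outcome is a session count, and no decision is tied to the 60% rule. The effect on the Bang index is small, and the plan sets no threshold for it. Severity is minor to should-fix.

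**What to change.** 1. In Section 4 (secondary outcome 2 and Table 1) and Section 8, use one name for the questionnaire. Give it and the blinding question once, after the tenth session or when sessions end early, to every subject who had at least one session and has not withdrawn or been removed. If missed, use the next scheduled remote contact or the REDCap survey link already described in Section 14, and record the date.
2. Keep all 20 randomised subjects as the denominator and state that no answer counts as not agreeing, including for a subject with no session. Also report the respondent-only proportion, with the number of and reasons for non-response.
3. Keep the 60% rule on item 11, label it *perceived benefit*, and report it by arm as well. Report items 1 to 10 (4, 5, 8 and 9 reverse coded) descriptively as acceptability.
4. Report the Bang index with the number asked per arm, and show late answers separately.

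**Cost.** Wording changes, plus one short questionnaire at a contact or link that already exists. Late answers may carry recall error, and late guesses may reflect perceived outcome. A subject who stops after session 1 and is asked only at the day-14 assessment answers 14 to 21 days later. Withdrawn subjects remain unasked.

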1. PURPOSE OF STUDY

Aim 1: To examine the feasibility of the home-based transcranial direct-current stimulation (tDCS) apparatus and protocol (as well as the home-based tDCS sham protocol) for future use as an adjunctive treatment to prevent suicidal ideation (SI) relapse in adult patients with mood or bipolar disorders after discharge from the Comprehensive Psychiatric Emergency Program (CPEP) or inpatient unit to which they were admitted with SI or attempt.

Hypothesis 1: We expect at least 70% of the subjects to complete at least 5 of recommended 10 RS-tDCS sessions within three weeks of receiving the home-based tDCS device.

Aim 2: To detect a preliminary signal of the effect of adjunctive home-based tDCS on indices of SI measured with The Columbia-Suicide Severity Rating Scale (C-SSRS) in adult patients with mood or bipolar disorders after discharge from the CPEP or inpatient unit of which they were admitted with SI or attempt.

Hypothesis 2: Subjects in the active tDCS arm will report less suicide ideation intensity (as measured by C-SSRS) than subjects in the control (sham) group at the end of treatment, which will help to determine an effect size for use in the sample size calculation for a full randomized controlled trial.

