5. INCLUSION AND EXCLUSION CRITERIA

Inclusion criteria:

- age between 18 and 65 years

- diagnosis of mood or bipolar disorder registered in the electronic hospital medical record

- history of suicidal ideation and/or suicide behavior at the time of admission registered in the electronic hospital medical record

- absent of suicidal ideation at the time of enrollment (defined as questions 1 and 2 of the C-SSRS answered "no").

- ability and willingness to provide information and permission to contact at least one person in the case of a need to contact them to promote subject safety or inability to reach the subject for follow-up

- a living situation with access to a private space suitable for administration of the RS-tDCS sessions in next three weeks

- agree to use a medically acceptable form of birth control while receiving the treatment if you are an individual able to become pregnant

- living in Monroe County region, as this is the area covered by the Mobile Crisis Team, a URMC psychiatric emergency team serving anyone within Monroe County

- device or computer with internet access for a URMC-approved remote RS-tDCS supervision

- ability to manage proper use of the device in a practice session

Exclusion criteria:

- acute psychiatric instability or substance abuse (e.g., psychotic symptoms, alcohol misuse in the previous three months, use of any illicit drugs in the previous three months)

- unstable medical condition with reduction of functional capacity

- history of epilepsy or seizures in the last year

- history of neurodegenerative diseases registered in the electronic hospital medical record
- presence of or implanted any ferromagnetic metal in the head or the neck
- pregnant or breastfeeding or willingness to become pregnant in the next month

- history of head trauma (e.g., head injury, brain injury) or neurosurgery
- history of skin disorder or sensitive skin area near stimulation locations
- the presence of pacemaker
- current treatment with electroconvulsive therapy or transcranial magnetic stimulation

Although concurrent treatment with medications or psychotherapy is not an exclusion criterion, we will measure changes in medication and psychotherapy for descriptive and planning purposes (please, see "Secondary outcome measures", item 9).

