16. DATA AND SAFETY MONITORING PLAN

Risk to study subjects is minimized by only employing well-trained and clinically experienced personnel. Routine hospital protocols are already in place for handling in-person and over-the-phone crises.

Adverse Events (AEs) and Serious Adverse Events (SAEs)

An adverse event is "any untoward or unfavorable medical occurrence in a human subject...temporally associated with the subject's participation in the research, whether or not considered related to the subject's participation in the research." A serious adverse event (SAE) is an event where a relationship to the research study cannot be ruled out, and the event is life-threatening/results in death OR disabling/incapacitating OR requires or prolongs hospitalization OR involves an overdose OR was otherwise unanticipated, related to the study procedures. Due to the nature of this study, suicide attempts and psychiatric hospitalizations are possible to

happen during its course. These events are considered SAEs and reported as such. In most circumstances, suicide attempts and psychiatric hospitalizations are expected for this population and, as a result, non-study related. As such, these SAEs will be reported at continuing review but only unexpected reported immediately to the IRB. Suicide deaths are reported to the IRB within 48 hours of learning of the death. In addition, the report includes investigators' judgment as to whether a relationship to the research study can/cannot be ruled out.

For all AEs, the date and time of onset and outcome, course, intensity, action is taken, and causality to study treatment will be assessed. Based on the review of the circumstances and as-needed consultation with co-investigators, the PI can reclassify an AE as an SAE. If considered related to the study, unanticipated adverse events involving risks to subjects or others will be reported by the PI to IRB. For each adverse event, the treatment groups are compared in a pair-wise fashion regarding the occurrence of at least one event using Fisher's exact tests; the numbers of individual events will also be described. All subjects are included in these analyses.

Confidentiality

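### Both C-SSRS efficacy outcomes rest on ideation answers at visits, with no rule for a subject who attempts suicide, dies by suicide or is readmitted for suicidality

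*Combined protocol and SAP*

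**What the plan says.** Subjects qualify through a "history of suicidal ideation and/or suicide behavior at the time of admission" (Section 5) and must be "absent of suicidal ideation at the time of enrollment", defined as 'no' to C-SSRS questions 1 and 2.

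Section 4 defines two C-SSRS outcomes, each read at days 14, 30 and 60 from the first session:

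- Secondary outcome 1 introduces the instrument with "The C-SSRS is a suicidal ideation and behavior rating scale with yes/no responses". The outcome itself is the sum of five ideation-intensity items, range 0 to 25.
- Secondary outcome 3 is the "Proportion of patients who answered 'no' for both questions 1" and 2. It is tied to relapse in these words: "This will help to determine the proportion of subjects who presented suicidal ideation relapse", the reason given being "since the negative answer for both questions will be an inclusion criterion for this study".

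Section 16 says that "suicide attempts and psychiatric hospitalizations are possible to" occur while the trial runs. It classes them as SAEs, and compares each adverse event between arms with Fisher's exact test in all subjects.

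Section 17 is the whole analysis plan. It gives a t-test or chi-square test at each time point. It states no denominator for outcome 3, no missing-data rule, and no rule for events that occur between visits or prevent one.

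**The concern.** Entry can be through suicidal behaviour, and the scale covers behaviour, but no efficacy outcome uses it. The study can know from its own SAE reports that a subject attempted suicide and still have no stated way to let that fact reach the relapse or intensity result.

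There are two distinct mechanisms. A subject who attempts and later attends, answering 'no' to both questions, counts as relapse-free at that visit; the measure is per visit, and no look-back period is stated. A subject who dies, or who cannot be assessed, has no answers at all. Section 13 adds another route to a missing score: subjects who start electroconvulsive therapy or transcranial magnetic stimulation are removed from the study. Missing scores may therefore be related to the outcome.

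What is at stake is the Aim 2 signal. Hypothesis 2 uses C-SSRS intensity at end of treatment to obtain an effect size for sizing a full trial, and outcome 3 describes relapse.

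**Working it through.** **Inputs from the protocol.** 20 subjects (Sections 4 and 17), randomised 1:1 (Section 4.1), so about 10 per arm; intensity range 0 to 25. No relapse rate, SD, effect size or power is given, so there is no planned figure to reproduce. The counts below are assumptions.

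**Relapse proportion.** Suppose 3 subjects in each arm answer 'yes' to question 1 or 2 at a visit, and 2 further sham subjects have an attempt, suicide death or readmission and no C-SSRS at that visit.

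| Rule for the two sham subjects | Active | Sham | Sham minus active |
|---|---|---|---|
| Available cases only | 3/10 = 30.0% | 3/8 = 37.5% | 7.5 points |
| All randomised, missing read as no relapse | 3/10 = 30% | 3/10 = 30% | 0 points |
| All randomised, relapse = everyone without two 'no' answers | (10 − 7)/10 = 30% | (10 − 5)/10 = 50% | 20 points |
| Events counted as relapse | 3/10 = 30% | (3 + 2)/10 = 50% | 20 points |

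With 1 to 3 such events in sham, the available-case difference runs from 3/9 − 3/10 = 3.3 points to 3/7 − 3/10 = 12.9 points. Counting events gives 10 to 30 points. If the events fall in the active arm, the signs reverse. With 2 in each arm the difference is 0 either way, but the available-case rate is 3/8 = 37.5% against 5/10 = 50%.

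**Attempters who attend.** If the same two sham subjects attend and answer 'no', the result is 3/10 v 3/10 whichever denominator is used. Only counting the event gives 5/10. One such subject moves an arm by 1/10 = 10 points.

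**Ordinary dropouts.** The third row recovers the events only by treating every missing answer as relapse. If 2 active subjects also miss the visit for unrelated reasons, active becomes (10 − 5)/10 = 50% and the difference falls to 0. Two is a plausible number if the 22% to 25% dropout cited in Section 17 carried over to assessments: 0.22 × 10 = 2.2 to 0.25 × 10 = 2.5 per arm. That figure is for home-based tDCS in bipolar depression, so carrying it over is an assumption.

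**Intensity.** If one of 10 subjects is unscored and the other nine have mean m, the t-test uses m. Assigning the unscored subject the maximum gives (9m + 25)/10, a shift of (25 − m)/10, which is at most 2.5 points (when m = 0).

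**Test result or estimate?** With 10 per arm, power for 50% v 30% at two-sided 0.05 is Φ[(√10 × 0.20 − 1.96 × √(2 × 0.40 × 0.60)) / √(0.50 × 0.50 + 0.30 × 0.70)] = Φ(−1.07) = 14%. For 5/10 v 3/10 the chi-square p is 0.36 and Fisher's p is 0.65. The handling rule changes the estimate and is unlikely to decide a test.

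**How many events?** A rough guide from Section 2, using figures from other populations. Suicide deaths: 263.9/100,000 × 20 × 60/365 = 0.009. Attempters, from almost 40% over 5 years: 20 × 0.40 × 60/(5 × 365) = 0.26 if spread evenly; if a quarter fell in the first month, 20 × 0.40 × 0.25 = 2.0 by day 30. Not every subject here enters after an attempt. No readmission rate is given.

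**The case against.** The strongest reply is that the plan need not lose these subjects from outcome 3. Someone who died did not answer 'no', and with all randomised subjects as denominator falls into the relapse group by complement. This stands. A reader might infer that the plan drops such subjects from the relapse proportion; the documents do not say so, because they state no denominator. The reply does not help the attempter who attends and answers 'no', and it does not supply a missing intensity score.

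A reader might also infer that readmission means a missed visit. That is not supported. Follow-up is remote (Table 1), aimed at phone contact with a survey link as fallback (Sections 8 and 14), has windows of 7 or 10 days, and readmission is not a listed reason for withdrawal.

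Nor are the events lost from the trial. They are compared by arm as adverse events in all subjects, and event review is itself secondary outcome 8. That protects the safety picture but does not alter the relapse proportion or the intensity mean.

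Finally, ideation alone may be intended: the aim, Hypothesis 2 and the name of outcome 3 all refer to ideation. This is a fair reason to keep the ideation-only result. It does not remove the need to say how a subject who dies, attempts or is readmitted is handled.

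**Conclusion.** The point holds as a gap in the two C-SSRS efficacy outcomes. An attempter who answers 'no' is scored relapse-free under any denominator. An unscored subject leaves the intensity t-test unless a value is assigned, and leaves the relapse proportion only if an available-case denominator is chosen.

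The size is illustrative. One subject is about 10 points in an arm of 10; two events in one arm can separate the estimates by 12.5 points (20 − 7.5) or by 20 points (20 − 0), depending on the rule. Event numbers may be as low as none. The direction depends on which arm the events fall in, so a claim that the plan favours active treatment is not supported.

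A reader might also infer that a biased relapse rate will size the next trial. Section 1 does not say that: what it takes forward is the effect size from intensity. This is a cheap improvement to secondary outcomes in a feasibility pilot; the primary feasibility criterion is untouched.

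**What to change.** 1. In Sections 4 and 17, state all randomised subjects as the denominator for outcome 3. Report missing answers by arm. For missing visits without a known event, show the result with them counted as relapse and as no relapse.
2. Keep the ideation-only proportion. Beside it, report relapse by each visit as any of the following since the first session: 'yes' to question 1 or 2, suicidal behaviour on the C-SSRS, suicide death, or psychiatric readmission for suicidal ideation or behaviour. Take the events from SAE reports and the hospital record.
3. For intensity, list by arm the subjects with such an event and no score. Add a sensitivity comparison that ranks them below every observed outcome, using a rank-sum test.
4. Leave out emergency visits without admission. The SAE definition in Section 16 does not name them, and the study's own risk assessments can lead to them (Section 9), so they would partly measure contact with study staff.

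The cost is outcome wording, one derived variable and one sensitivity analysis. SAEs are already recorded, and consent covers records on admission dates, ideation and self-harm (Section 7); the team should confirm that this access runs through follow-up. The downside is a broader supplementary endpoint and possibly higher reported relapse rates. No clinical procedure changes.
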